### 12.3 Analysis of Secondary Endpoints

Secondary endpoints will also be analyzed in a similarly descriptive manner. Treatment completion rate is defined by the administration of all eight intended cycles of neoadjuvant chemotherapy. The surgical complete resection rate (R0) will be determined from review of the pathology reports and inclusive of pathologic nodal status and TNM staging (AJCC 8th Edition). Pre-operative imaging will be compared to the baseline studies to assess radiographic response, in those who have RECIST measurable disease at baseline. The radiographic objective response rate (RR) is equal to the proportion of patients achieving a best overall response of partial or complete response (CR + PR), according to RECIST from the start of the treatment until disease progression/recurrence. Clinical benefit rate is equal to the objective RR plus the proportion of patients attaining stable disease (CR + PR + SD). Patients with initially measurable disease who do not have a tumor response assessment for any reason will be considered non-responders and will be included in the denominator when calculating the response rate. Biochemical response rate is measured as

the difference between baseline and maximal nadir of serum CA19-9 level. Proportion and exact 95% CI based on binomial distribution will be estimated for each of the secondary endpoints described above. Subjects will further be characterized as those with normalization of CA19-9 during therapy, reduction without normalization or no reduction with assessment of the temporal nature of these changes and correlation to surgical resection rates. Secondary and exploratory endpoints may be characterized between those with resectable vs. borderline resectable disease at study entry, but without any planned formal analyses between these two subsets. Mean and 95% CI, assuming a normal distribution, median (range) will be estimated for quality of life (QOL) parameters using the FACT-G validated patient reported outcome instrument.

#### 12.4 Analysis of Exploratory Endpoints

Exploratory biomarkers and molecular assay results will be analyzed post-hoc. These assessments are dependent upon funding support for determination including, but not limited to CTC enumeration and correlation with pathologic/radiographic response, pharmacogenomic determination of any relationship with toxicity/safety, tumor mutational profile assessments correlating with response vs. non-response as well as PDX development with supplemental correlative analyses to determine mechanisms of response and resistance.

#### 12.5 Analysis of Safety Data

Safety analyses will be performed on all patients who receive any dose of study medication. Adverse events that occur more than 30 days after the administration of the last dose of treatment will not be included. Safety evaluation will be performed based on the actual therapy received. The safety and tolerability of study drug is determined by reported Aes, physical examinations, laboratory tests, and ECGs. All patients will be assessed regularly for potential occurrence of Aes from the time that treatment starts until 30 days after the last dose of study therapy or 30 days post-operatively, whichever is longer. Aes will be summarized with the incidence and percentage of patients with at least one occurrence of a preferred term (according to the most severe NCI-CTCAE Version 4.0 grade) will be included. The number of Aes reported will also be summarized. Causality (relationship to study drug) will be summarized separately. Duration of AE will be determined and included in listings along with action taken and outcome. Laboratory results will be classified according to NCI-CTCAE, Version 4.0. Incidence of laboratory abnormalities will be summarized; laboratory results not corresponding to an NCI-CTCAE Version 4.0 term will not be graded. Laboratory toxicity shifts from baseline to worst grade will also be provided. The results from physical examination and vital sign measurement will be tabulated. Descriptive statistics will be provided as appropriate.

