#### 11.1.2 Serious Adverse Event

A serious adverse event is one that at any dose of the study drug or at any time during the period of observation:

- Results in death
- Is life-threatening (defined as an event in which the subject was at risk of death at the time of the event; it does not refer to an event which hypothetically might have caused death if it were more severe)
- Requires inpatient hospitalization or causes prolongation of existing hospitalization (see note below for exceptions)
- Results in persistent or significant disability/incapacity
- Is a congenital anomaly/birth defect
- Is an important medical event, defined as a medical event that may not be immediately life-threatening or result in death or hospitalization but, based on appropriate medical and scientific judgment, may jeopardize the subject or may require intervention (e.g., medical, surgical) to prevent one of the other serious outcomes listed above. Examples of such events include but are not limited to intensive treatment in an emergency department or at home for allergic bronchospasm; blood dyscrasias or convulsions that do not result in hospitalization. “Medically important” should be marked only if no other serious criteria are met.

An “unexpected SAE” is any SAE for which the nature, specificity or severity is not consistent with the currently known adverse event profile of the investigational agent(s).

**NOTE:** The following hospitalizations are not considered SAEs in UFHCC clinical studies:

- a visit to the emergency room or other hospital department lasting less than 24 hours that does not result in admission (unless considered an “important medical event” or a life-threatening event)
- elective surgery planned before signing consent
- admissions as per protocol for a planned medical/surgical procedure
- routine health assessment requiring admission for baseline/trending of health status (e.g., routine colonoscopy)
- medical/surgical admission for purpose other than remedying ill health state that was planned before study entry. Appropriate documentation is required in these cases.
- admission encountered for another life circumstance that carries no bearing on health status and requires no medical/surgical intervention (e.g., lack of housing, economic inadequacy, caregiver respite, family circumstances, administrative).

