### 11.2 Period of Observation

Following the subject's written consent to participate in the study, all SAEs must be collected, including those thought to be associated with protocol-specified procedures. Collection of all SAEs must continue until the post-op visit (or pre-op visit if the subject does not proceed with surgery). If applicable, SAEs must be collected that relate to any later protocol-specified procedure (e.g., protocol-specified resection surgery). SAEs not related to a later protocol-specified procedure will not be collected beyond 30 days post last dose of study treatment. The investigator should notify the DISC of any SAE occurring after this time period that is believed to be related to the investigational product or protocol-specified procedure.

The investigator will begin collecting non-serious adverse event (NSAE) information once administration of the investigational product is initiated. This NSAE information should also be collected from the start of a placebo lead-in period or other observational period intended to establish a baseline status for the subjects. Treated subjects, including those who were prematurely discontinued from the study, will be followed for any adverse events that occur during the study until the post-op visit (or pre-op visit if the subject does not proceed with surgery). However, after 30 days post last dose of study treatment, only unexpected AEs related to a protocol-specified procedure (e.g. resection surgery and associated hospitalization) will be reported. If another course of anti-cancer therapy is initiated prior to the that follow-up period visit, collection of adverse events will no longer be performed, with the exception of events that may be possibly, probably, or definitely related to the investigational agent or are clinically significant.

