### 12.2 Analysis of Primary Endpoint

The primary analysis will use the modified Intention-to-Treat (mITT) population consisting of subjects who are enrolled and received any dose of study medication. The mITT population will be included in summary tables of subject demographics and disease characteristics, and in analysis of efficacy. Subjects who did not progress to surgery (for any reason) or are lost to follow-up will be censored at the day of their last objective tumor assessment and will be unevaluable for the primary endpoint. Subjects failing to proceed to surgery will be replaced, but all will support the secondary endpoints including feasibility, safety and correlative biologic analyses.

Post-operative complications will be measured at the EOT visit 4-6 weeks after surgery. Complications occurring within 30 days after surgery and contributing to the primary endpoint are defined as hospital re-admission, death, second surgery or interventional procedure or major complications extending hospital stay. The proportion and its exact 90% confidence interval of 30-day post-operative complication rate will be calculated. Statistical analyses will be conducted using SAS v9.4 (SAS institute, Cary, NC).

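### Section 12.5 closes the adverse event tables 30 days after the last dose, so almost none of the 30 post-operative days is tabulated, although 11.2 requires resection-related events from that period

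*Combined protocol and SAP*

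**What the plan says.** Section 12.5 takes all treated patients as the safety population and then sets the cut-off: "Adverse events that occur more than 30 days after the administration of the last dose of treatment will not be included". It makes no exception for surgery. A few lines later it has patients assessed for AEs "until 30 days after the last dose of study therapy or 30 days post-operatively, whichever is longer". The planned summaries are by preferred term and worst CTCAE grade, with causality summarised separately.

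The synopsis (Efficacy Assessments) and the overall treatment plan in 7.1 place surgery 4 to 8 weeks after the last chemotherapy dose. Where radiotherapy is given, 7.2.4 places it 4 to 8 weeks after that.

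Section 11.2 says what is collected later than 30 days after the last dose:

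- On SAEs tied to the operation: "SAEs must be collected that relate to any later protocol-specified procedure (e.g., protocol-specified resection surgery".
- On other SAEs: "SAEs not related to a later protocol-specified procedure will not be collected beyond 30 days post last dose of study treatment".
- On remaining AEs: "only unexpected AEs related to a protocol-specified procedure (e.g. resection surgery and associated hospitalization) will be reported".
- On late drug-related SAEs: "The investigator should notify the DISC of any SAE occurring after this time period that is believed to be related to the investigational product".

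The same section also has SAE collection in general running on to the post-operative visit. It keeps possibly drug-related or clinically significant events after a new anti-cancer therapy starts.

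Section 12.2 counts complications within 30 days of surgery, "defined as hospital re-admission, death, second surgery or interventional procedure or major complications extending hospital stay", and reports them as one proportion with an exact 90% confidence interval.

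**The concern.** The synopsis names perioperative safety as the main goal of the strategy, yet the cut-off in 12.5 closes the AE tables at about the time the earliest operations take place. The section's two time limits cannot both define the tables.

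Death is an SAE criterion in 11.1.2, and so is an event that "Requires inpatient hospitalization or causes prolongation of existing hospitalization". A death, re-admission or prolonged stay caused by the resection is therefore an SAE that 11.2 requires, and 12.5 then leaves it out. The report would give a complication rate without the matching terms, grades and causality in the AE tables. A procedure-related SAE or unexpected AE that falls outside the 12.2 composite would appear in neither analysis.

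**Working it through.** **Inputs.** Table cut-off: day 30 after the last dose (12.5). Surgery day s: 28 to 56 (synopsis, 7.1), so 56 − 28 + 1 = 29 possible days. Post-operative window: 30 days (12.2, 12.5). 5-FU infusion: 46 hours (Table 3.1). Radiotherapy: 45 to 54 Gy at 1.8 Gy per fraction (7.2.4). Complication rates: 10% and 30%, in 25 operated subjects (12.1). The plan states no figure for this overlap, so there is none to reproduce.

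**Overlap without radiotherapy.**

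| Counting rule | Post-operative days inside the tables | Maximum (s = 28) | Surgery days with none |
|---|---|---|---|
| Post-operative days 1–30 | max(0, 30 − s) | 2 | 27 of 29 |
| Day of surgery also counted | max(0, 31 − s) | 3 | 26 of 29 |
| Clock from end of infusion (about 2 days later) | max(0, 32 − s) | 4 | 25 of 29 |
| Both | max(0, 33 − s) | 5 | 24 of 29 |

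On the first rule, s = 28 gives 2 days, s = 29 gives 1, and s = 30 to 56 gives 0. If surgery days were spread evenly over the range (an assumption), the share of post-operative days covered would be (2 + 1)/(29 × 30) = 3/870 = 0.34%.

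**Overlap after radiotherapy.** A conventional course is 45/1.8 = 25 to 54/1.8 = 30 fractions. At one fraction a day (assumed) and starting after the last NALIRIFOX dose, surgery comes no earlier than day 25 + 28 = 53, so no post-operative day is inside the cut-off. Short-course schedules are allowed, but the protocol gives no fraction count for them. If radiotherapy itself counts as the last treatment, the table above applies again from its last dose.

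**Effect of using 12.5's own assessment window.** The tables would close on day 28 + 30 = 58 to day 56 + 30 = 86 instead of day 30, and all 30 post-operative days would be covered.

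**Are there likely to be events to lose?** Expected subjects with a 12.2 complication: 25 × 0.10 = 2.5 to 25 × 0.30 = 7.5. Chance of at least one: 1 − 0.9^25 = 0.928 at 10%, and 1 − 0.7^25 = 0.9999 at 30%.

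**Limit of the data.** The post-operative visit is 4 to 6 weeks after surgery (6.4). At 4 weeks it falls on post-operative day 28, 2 days before the 30-day window ends.

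**The case against.** The strongest reply is that post-operative safety already has its own analysis in 12.2, and that oversight does not depend on the tables. SAEs go to the safety committee and the project office on short timelines (11.4.1), and the suspension rule in 12.6 has no day-30 limit. Section 12.5 can also be read as a study-drug tolerability analysis, for which a window tied to the last dose is coherent. Because 11.2 restricts what is collected after day 30, an incidence table for that period would be incomplete.

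Much of this stands. A reader might infer that the cut-off damages the primary endpoint or leaves surgical complications unanalysed; 12.2 shows otherwise. A reader might also infer that 12.5 discards all post-operative AEs. It cannot, because 11.2 does not ask for expected non-serious events after day 30. The opposite inference, that unrelated SAEs are certainly not collected after day 30, is also too firm, because another sentence in 11.2 continues all SAE collection to the post-operative visit. For late drug-related SAEs, 11.2 requires notification to the committee but does not say whether they enter the trial database.

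The reply does not remove the conflict. Section 12.5 is the only planned AE tabulation, and its own assessment window runs to post-operative day 30. Neither the composite proportion nor committee review supplies terms, grades and causality. Incomplete collection calls for a footnote; it does not justify leaving out events that the protocol requires.

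**Conclusion.** The point holds as a conflict within 12.5 and between 12.5 and 11.2. At most about 2 of the 30 post-operative days are tabulated, up to 5 on the most generous count. On the plain count there are none for surgery on day 30 or later, and none after a conventional radiotherapy course counted from the last NALIRIFOX dose. This rests on surgery taking place on day 28 to 56. The pre-surgical timing in 6.3 would permit later surgery, which only widens the gap.

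What is lost is the tabulation by preferred term, grade and causality of the resection-related SAEs and unexpected procedure-related AEs that 11.2 requires, together with any such event outside the 12.2 composite. It is tempting to read the 2.5 to 7.5 subjects as the number of SAEs missing from the tables. They are not: they are composite events, still counted under 12.2, and the composite does not require relation to the resection. They show only that resection-related SAEs are likely to occur. The documents give no rate for other post-operative SAEs or unexpected AEs, so the number lost cannot be estimated.

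The primary endpoint is intact. The AE wording should be corrected before the tables are programmed.

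**What to change.** In 12.5, replace the exclusion sentence with: *AEs with onset from first dose to the later of 30 days after the last dose or 30 days post-operatively will be included.* Summarise two periods separately:

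- (a) On treatment: first dose to the earlier of 30 days after the last dose or the day before surgery, in all treated subjects (to 30 days after the last dose where there is no surgery).
- (b) Post-operative: day of surgery to post-operative day 30, in operated subjects.

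List any collected events that fall between the two periods. Footnote (b): *Collection of events more than 30 days after the last dose is restricted under section 11.2 and ends at the post-op visit, so this is not a full count of post-operative AEs.*

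In 11.2, reconcile the sentence that continues all SAE collection to the post-operative visit with the one that stops unrelated SAEs at 30 days.

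The cost is one sentence in 12.5, one more set of tables, a short listing, a footnote and a wording correction in 11.2. Tabulating what 11.2 already requires needs no new visits. The downside is a little more tabulation, and table (b) must be read with its footnote.

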The toxicity profile of irinotecan liposomal injection (ONIVYDE®) with 5-fluorouracil and leucovorin in the second line metastatic setting is very reasonable with the added benefit of improved drug delivery to tumor. In the neoadjuvant setting, where patient toxicity is paramount and tumor vasculature is undisrupted, the incorporation of ONIVYDE® could have an important anti-neoplastic effect by improved biologic drug delivery and improved full treatment compliance. Delivering a complete (4 month) course of systemic therapy with maintenance of patient health and minimization of post-op complications would represent a clinically significant step forward in the field of pancreatic cancer therapy.

[figure not shown]
This protocol aims to substitute irinotecan liposomal injection (ONIVYDE®) for traditional irinotecan in the standard FOLFIRINOX regimen and deliver the therapy in the neoadjuvant setting. The primary goal of this strategy is to rapidly establish perioperative safety with regards to surgical outcomes. The doses and schedule will be those established by the safety run-in/Arm 1 of the currently enrolling randomized phase II front-line study in metastatic pancreatic cancer (NCT02551991). Recent safety data from that study supports the incorporation of ONIVYDE in this combination for previously untreated patients with metastatic pancreatic cancer. This study will also help establish a benchmark for radiographic response rate, pathologic down staging and treatment compliance. Potential post-hoc correlative analyses include, but are not limited to, assessment of pancreatic cancer circulating tumor cells associated with treatment response, development of patient-derived cell lines and xenografts from refractory tumor removed at the time of surgical resection to determine pathways of resistance and microenvironmental immunosuppression, comprehensive mutational profiling of pancreatic adenocarcinoma tissue and pharmacologic precision medicine program assessments of novel pharmacogenomic profiles (e.g., additional haplotypes of UGT1A1, as well as UGT1A7, ABCG2/B1/C2, and SLCO1B1) associated with irinotecan-associated GI toxicity and myelosuppression. Taken together, this study will support continued development of this novel combination regimen in the adjuvant, perioperative or metastatic setting.

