#### Overall treatment plan

- ONIVYDE® with 5-fluorouracil, leucovorin and oxaliplatin (NALIRIFOX) at the recommended for phase II doses determined from NCT02551991-IV dosing every 2 weeks x 8 total treatments (4 months)
- Surgical resection in the absence of documented progression within 4-8 weeks following last dose of therapy. Clinical response assessment following last cycle of NALIRIFOX.
- Optional chemoradiotherapy with evidence of local disease progression or as otherwise defined in Section 7.2.4
- Optimal supportive care and growth factor support per recommendations from NCT02551991
- Clinical follow-up 4-6 weeks post-operatively (EOT visit)
- Survival follow-up every 6 months for 5 years and documentation of any recurrence.

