**IMRT / IGRT Radiotherapy Prescription:**

CTV1: 45 - 50.4 Gy at 1.8 Gy/Fx to >95% PTV

CTV2: (GTV Boost) Final Dose of 50.4 – 54 Gy at 1.8 Gy/Fx to >95% PTV

Concomitant infusional 5-FU or daily capecitabine, per NCCN guidelines and institutional practice, is strongly recommended.

Alternative radiotherapy dosing with short course or SBRT, or proton therapy, may be considered upon review of the case, at the discretion of the PI and with consultation of radiotherapy sub-investigators.

In any situation requiring radiotherapy, surgery should still be planned 4-8 weeks after the last dose of chemoradiotherapy or radiotherapy. Please note additional consideration for pre-surgical imaging assessments in the Scheduled of Events (Appendix A), as an additional assessment may be required after completion of radiotherapy.

Otherwise, radiotherapy use is prohibited during study treatment. Patients may undergo post-operative radiotherapy after completing the EOT assessment if surgical resection resulted in a positive margin or other feature that justifies this modality. If a patient has radiographic progression of disease that renders them inoperable or they develop metastatic disease during the course of study treatment, these patients will be removed from study and can be treated per institutional practice.

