Section 6.1, 6.2, 6.3, Appendix A	
 
• Updated so ECGs past baseline/screening will only be performed if medically indicated, and to document any abnormalities at the screening ECG
 

Sections 6.4, 9.2, Appendix A Footnote 11	
 
• Added Microbiota collection information
 

Section 7.2.2, 11.2, 11.3, Appendix A Footnote 10	
 
• Updated collection of Concomitant Medications and Adverse Events after 30 days post last dose to capture complications of surgery
 

Section 7.3	
 
• Added language that Oxaliplatin may be discontinued while subject remains on study
 

Section 16	
 
• Added reference #38 for NCT 02551991 study
 

Appendix A Footnote 2	
 
• Removed uric acid, added albumin
 

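### Section 12.5 assesses adverse events to 30 days after surgery but cuts the safety tables at 30 days after the last dose, which leaves at most about two post-operative days inside them

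*Combined protocol and SAP*

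**What the plan says.** **Section 12.5** covers everyone who receives any study medication and gives two windows.

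- Analysis: "Adverse events that occur more than 30 days after the administration of the last dose of treatment will not be included".
- Assessment: patients are followed for AEs "until 30 days after the last dose of study therapy or 30 days post-operatively, whichever is longer".

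The section makes no exception for surgery and does not say which window governs. It is also where the AE displays are planned: incidence by preferred term at worst CTCAE grade, causality, and listings with duration, action taken and outcome.

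**Timing of surgery.** The overall treatment plan in Section 7.1 has "Surgical resection in the absence of documented progression within 4-8 weeks following last dose of therapy", and the synopsis gives the same interval. If the optional radiotherapy of Section 7.2.4 is used, "surgery should still be planned 4-8 weeks after the last dose of chemoradiotherapy or radiotherapy".

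**Collection.** Section 11.2 says "Collection of all SAEs must continue until the post-op visit", then narrows this. Beyond 30 days from the last dose, SAEs are dropped unless they relate to a later protocol procedure, and other AEs are reported only if they are unexpected and related to such a procedure. One criterion for seriousness in Section 11.1.2 is "Requires inpatient hospitalization or causes prolongation of existing hospitalization".

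**Primary endpoint.** Section 12.2 counts readmission, death, re-operation or intervention, and stay-extending major complications within 30 days of surgery. It reports them as one proportion with an exact 90% interval.

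**Intent.** Section 1.2 states: "The primary goal of this strategy is to rapidly establish perioperative safety with regards to surgical outcomes". The summary of changes from version 5.3 to version 6 (Appendix I) records: "Updated collection of Concomitant Medications and Adverse Events after 30 days post last dose to capture complications of surgery". I use that log entry only as a sign of intent; the conflict lies wholly in current text.

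**The concern.** The resection happens at about the point where the analysis window closes. One programmer could follow the exclusion sentence and stop the AE tables at day 30 after the last dose. Another could follow the assessment sentence and run them to post-operative day 30. Both could cite Section 12.5, and they would produce different tables from the same data.

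The composite in Section 12.2 shows how many operated subjects had a major complication. It does not show what the events were, how severe they were, or whether they were attributed to study drug. Section 1.1 treats delayed gastric emptying, bile leak and pancreatic fistula as separate risks of this operation. The displays that could separate such events are those of Section 12.5, and read literally its exclusion removes them. That sits badly with a trial whose stated goal concerns surgical outcomes.

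**Working it through.** The plan gives no figure to reproduce here, so the check is an overlap of two windows.

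**Inputs**

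- Analysis cut-off: day 30 after the last dose (Section 12.5).
- Day of surgery, S: 4 × 7 = 28 to 8 × 7 = 56 after the last dose (Section 7.1), which is 29 possible days.
- Post-operative period: 30 days after surgery (Sections 12.2 and 12.5).

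**Step 1. Overlap.** Post-operative day k falls on day S + k after the last dose and is included only if S + k ≤ 30. The number of post-operative days 1–30 included is therefore max(0, 30 − S). Counting the day of surgery, it is max(0, 31 − S).

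| Surgery on day S | Post-operative days 1–30 included | Same, counting the day of surgery |
|---|---|---|
| 28 | 2 of 30 | 3 of 31 |
| 29 | 1 of 30 | 2 of 31 |
| 30 | 0 of 30 | 1 of 31 |
| 31 to 56 | 0 of 30 | 0 of 31 |

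**Step 2. Radiotherapy.** The standard prescription is 50.4/1.8 = 28 to 54/1.8 = 30 fractions. At five per week (assumed) that takes 38 to 40 days. Surgery then comes no earlier than day 38 + 28 = 66 to 40 + 28 = 68 after the last study-drug dose, and the overlap is zero. If the last radiotherapy dose is instead read as the last dose of treatment, the gap is again 28 to 56 days and the table above applies.

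**Step 3. How firm is the share lost?** The documents give no distribution of surgery dates or of AE onset, so any percentage is conditional.

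- Surgery equally likely on each of the 29 days, all post-operative days weighted equally: 3/(29 × 30) = 3/870 = 0.3% of days included, or 6/(29 × 31) = 6/899 = 0.7% counting the day of surgery.
- Same surgery dates, with onset concentrated early (weight exp(−d/m) on days d = 0 to 30, m from 3 to 15 days): 4.8% of events included at m = 3 and 1.5% at m = 15.
- Extreme case, every operation on day 28: 63% included at m = 3 and 21% at m = 15.

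The limits in Step 1 follow from the text. The share of events lost would be moderate rather than near-total only if operations clustered in the first days of the permitted window.

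**Step 4. Which events are affected?** For events after surgery and more than 30 days after the last dose:

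| Event | Collected under 11.2 | Counted in 12.2 | In 12.5 tables as written |
|---|---|---|---|
| Procedure-related SAE (death, readmission, prolonged stay) | Yes | Yes, if it meets the composite definition within 30 days of surgery | No |
| Unexpected non-serious AE related to the procedure | Yes | Only if it meets a composite criterion | No |
| Expected non-serious AE | No | Only if it meets a composite criterion | No |

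The exclusion sentence is what removes the first two rows from the safety tables. The third row is already removed by the collection rule.

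**Step 5. After correction.** With the later of the two limits, the window closes at day 28 + 30 = 58 to 56 + 30 = 86 after the last dose. It then spans the full 30 post-operative days for every operated subject without radiotherapy, and likewise 30 days past surgery for those with it.

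**The case against.** The best defence is that Section 12.5 concerns the safety and tolerability of study drug, for which a 30-day limit is reasonable, and that surgical morbidity belongs elsewhere. On this view the longer assessment window is surveillance that feeds the primary endpoint. The major post-operative outcomes are counted there with no last-dose limit. Section 11.2 also restricts what is collected after day 30, so changing Section 12.5 cannot produce complete post-operative AE rates.

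Much of this stands. The primary analysis is intact, there is good reason to keep surgical events apart from drug toxicity, and the collection limit is real. What does not follow is that the conflict disappears. Section 12.5 itself extends AE assessment to 30 days post-operatively and names no other place for those events. A separate column keeps the two kinds of event apart without discarding one.

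Two stronger readings are tempting, and the documents support neither.

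- A reader might infer that perioperative safety, or a post-operative death, would go unreported. A death within 30 days of surgery counts in the Section 12.2 composite, and Section 11.4.1 requires SAEs to be reported to the safety committee's team.
- A reader might infer that all the data exist and only the analysis rule discards them. That is untrue of expected non-serious AEs, which Section 11.2 does not have reported after day 30.

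**Conclusion.** The point holds as an internal inconsistency in Section 12.5 with a practical effect on the safety tables. For operated subjects, at most about the first two post-operative days fall inside the analysis window, and none do if surgery is after day 30. This rests on the planned 28-to-56-day interval and on reading the exclusion sentence literally. It does not depend on an assumed pattern of surgery dates.

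The loss is confined to descriptive displays: the preferred term, grade, causality and outcome of procedure-related SAEs (including deaths, readmissions and prolonged hospitalizations) and of unexpected procedure-related AEs. Subjects who never reach surgery have no post-operative period and are not affected. The 30-day complication rate, its interval and the sample size are untouched. The correction is worth making before the tables are programmed.

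**What to change.** In Section 12.5, replace the exclusion sentence with: *Adverse events up to 30 days after the last dose or 30 days post-operatively, whichever is later, will be included.*

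Show events from surgery to post-operative day 30 in a separate column, with operated subjects as denominator. Footnote it: *AEs as collected under Section 11.2; expected non-serious AEs after day 30 are not collected.* Without that note the column could be mistaken for complete post-operative incidence.

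Optionally, add to Section 12.2 a descriptive n/N for each component of the composite, including death, with no test.

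The cost is one corrected sentence and one extra table column, using data already collected under Section 11.2. The drawback is that capture in that column is selective. Complete post-operative incidence would need Section 11.2 to be amended as well, which this fix does not require. No alpha is spent, and the primary estimate, test and sample size stay as they are.
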